2. STUDY DESIGN

Study design: Single-blind study. Patients will be randomized, to LLTS versus sham procedure, and remain blinded to their treatment allocation. Both treatment options will utilize similar equipment, namely the use of alligator clips which will be placed on the tragus and earlobe of the right ear for patients (see Appendix A, Figure 2). The distinction is only that in patients assigned to LLTS, they will be initiated on therapy at the time of device placement.

Prior to cardiac surgery, the discomfort threshold of both left and right tragus stimulation will be determined for all participating patients. Intermittent electrode signals, or microcurrents, are delivered at 20 Hz with 200 μ sec pulse width with variable microampere (mA) output. The discomfort threshold is defined as the stimulation intensity in mA at which point patients experience discomfort. The stimulation intensity used in the study will be set just below the discomfort threshold, as established from prior work.¹⁵ The clip will then be placed on the patient's ear at the end of surgery. After surgery is completed, the clip will then be removed and replaced on the contralateral ear. Stimulation will then continue, one ear alternating with the other, every 4 hours for a total of 48 hours. It is possible that the threshold can change during the post-operative period. If the patient shows any sign of discomfort from stimulation, the intensity of stimulation will be reduced to a level at which signs of discomfort disappears.

Follow-up will be performed with 14-day event monitor (i.e. Zio patch or CardioNet event monitor) at the time of discharge.

Electrocardiography (i.e. ECG) will be performed pre-procedure and prior to hospital discharge. Echocardiography will be assessed prior to study initiation and when clinically available in follow-up.

Duration of study: 1 month

Primary endpoints: A combination of clinical and electrocardiographic endpoints will be prospectively studied. These include:

- **Clinical:** Primary clinical endpoint is time to inpatient AF (length of stay >5 days). Secondary endpoint is any occurrence of AF during 14 day post procedure monitoring.
- **Electrocardiographic:** Arrhythmia occurrence (i.e., AF, nonsustained VT, VT or VF requiring device therapy) will be documented throughout the study period

Primary safety endpoint: Procedure-related complications will be assessed prospectively both acutely and throughout the study period, including:

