5. STUDY PROCEDURES

Pre-Stimulation:

- Patients will be screened for study
- Discomfort threshold bilaterally will be measured (20 Hz) for 5 minutes
- Pre-implant ECG reviewed (to be performed on day of screening)
- Baseline transthoracic echocardiogram (TTE) reviewed (does *not* need to be performed during inpatient hospitalization; outpatient or outside-hospital TTE report may also be performed)
- NYHA functional class to be determined by treating physician
- Operating physician will be informed of patient randomization allocation to facilitate planning of procedure

Randomization, Implant, and Periprocedure Care:

- LLTS or sham will instituted upon arrival in PACU/recovery after surgery with right sided LLTS. The site of stimulation will alternate every 4 hours between right and left tragus for total stimulation duration of 48 hours.
- Postoperative care for the cardiac surgical patient will be performed as per routine standard of care by the treating primary team
- The patient will be maintained on telemetry during the entire inpatient hospitalization
- Telemetry will be checked daily to evaluate for any new-onset AF
- Predischarge ECG will be performed at the time of hospital discharge
- The patient will be fitted with a 14-day event monitor (i.e. Zio patch or Cardionet monitor) at the time of discharge or to be mailed to the patient/picked-up by patient immediately after discharge on a weekend discharge day
- Blood will be collected for C-reactive protein measurement to assess inflammation per routine lab assessments

Follow-Up Visit (can be performed between 2 weeks and 1 month after discharge):

- The patient will return the 14-day monitor, if not already mailed back
- Routine clinical check as per primary team

Future contact:

- Patients will be asked to participate in an extended registry (protocol IRB16-0272) to evaluate longer-term clinical outcome after study completion. Patients will be asked to sign a separate consent form for participation in this study.

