6. STATISTICAL PLAN AND CONSIDERATIONS

Primary Outcome:

1. Time to the first episode of AF >30 seconds during inpatient admission or within 14-day monitoring period

- a. In hospital: full-disclosure telemetry
- b. Time to AF will be assessed by physicians blinded to randomization
- 2. Extended hospitalization of >5 days

Secondary Outcomes:

- 1. Overall AF burden, as assessed by 2 week monitor (CardioNet or Zio Patch) upon discharge
- 2. Inflammatory markers: C-reactive protein (ordered if clinically indicated)
- 3. Actionable AF: antiarrhythmic use (including rate-control meds), CDV, anticoagulation, use of inotropes for BP support during AF
- 4. Stroke or transient ischemic attack (TIA)
- 5. All cause of mortality

Sample size estimation:

Assuming a two-armed study with composite endpoint of occurrence of AF or >5 days hospitalization, whereby the treatment group will have 50% likelihood of the event occurring and a control group will have 20% likelihood of the event occurring, as well as a 10% dropout rate, we will be able to detect differences in 80 patients (40 in each arm). Under these assumptions and using two-sided Z-Test with unpooled variance to compare the changes between these two groups, we will have 80% power ($\alpha=0.05$) to detect a difference between the group proportions of 0.30. PASS software Version 15 (NCSS, LLC, Kaysville, UT) was used to calculate the statistical power.

Statistical methods:

Patients will be studied based on the randomization allocation. Patients who refuse to continue with study treatment (i.e. they refuse to wear ear clip) during time of therapy will be analyzed as intention-to-treat per allocation group. Fisher's exact or the Chi-Square test will be used for categorical variables, and continuous parameters will be compared by the two-tailed unpaired Student's t test and the F test for analysis of variance (ANOVA), as needed. Kaplan-Meier method will be used for computing the event free survival curves. Each strategy will be compared within this cohort of patients for its impact on percent incidence of POAF and length of stay. Multiple logistic regression and multiple regressions using the Cox proportional hazards model will be performed to determine the independent association of each of the demographic variables with clinical outcome.

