15. APPENDIXES

A. FIGURES

Figure 1: Parasymp Device

Figure 2: Electrode attached to tragus

B. J AM COLL CARDIOL 2015;65:867–75

 Low-level
transcutaneous stimu

C. SCHEDULE OF EVENTS (SCHEMA)

	Screening	Surgery (Day 0)	Post-Op Days 1-2	Day of Discharge	Follow-Up Visit (2 weeks to 1 month after discharge)
Medical Records Review	X				X
Clinical Evaluation (Physical Exam, Vital Signs, Medication Review)	X	X	X	X	X
Electrocardiogram	X			X	
Echocardiogram	X ^a				X ^a
Urine Pregnancy Test	X ^b				
NYHA Functional Class Determination	X				
Randomization	X ^c				
LLTS or Sham Application		X ^d	X ^e		
C-Reactive Protein Blood Test		X ^f	X ^f		
Event Monitor (i.e. Zio Patch or Cardionet Monitor)				X ^g	X
Adverse Events		X	X	X	X

^a Results from records review, if available

^b Only for women of childbearing potential

^c Pre-procedure to facilitate planning of procedure

^d Immediately after surgery

^e Continuous for 48 hours

^f If clinically indicated

^g Pre-discharge if discharged on a weekday; arrangement for mailing or pick-up for patients discharged on a weekend day

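### Patients discharged at a weekend get the rhythm monitor only after leaving, so AF goes unrecorded between telemetry and first wear; the likely effect is small and the remedy cheap

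*Combined protocol and SAP*

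**What the plan says.** In-hospital cover is complete. Section 5 states: "The patient will be maintained on telemetry during the entire inpatient hospitalization".

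Outpatient cover depends on the day of discharge. Section 5 has the monitor fitted "at the time of discharge or to be mailed to the patient/picked-up by patient immediately after discharge on a weekend discharge day". Footnote g to the schedule of events (Section 15, Appendix C) repeats the rule: "Pre-discharge if discharged on a weekday; arrangement for mailing or pick-up for patients discharged on a weekend day".

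The follow-up visit is timed from discharge, not from the start of wear: "Follow-Up Visit (can be performed between 2 weeks and 1 month after discharge". At that visit, "The patient will return the 14-day monitor, if not already mailed back".

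The endpoint that these recordings serve is defined in two ways:
- Section 6, primary outcome: "Time to the first episode of AF >30 seconds during inpatient admission or within 14-day monitoring period".
- Section 2, primary: "Primary clinical endpoint is time to inpatient AF (length of stay >5 days". Section 2 then makes the 14-day result secondary: "Secondary endpoint is any occurrence of AF during 14 day post procedure monitoring".

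The documents set no maximum delay before the monitor is worn and no minimum wear time. They do not ask for the application date and give no rule for unmonitored time in the analysis.

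**The concern.** The Section 6 outcome relies on two recordings, telemetry and then the monitor. For weekday discharges they join without a break. For weekend discharges the protocol itself separates them, because a mailed or collected device cannot be worn as the patient leaves the ward. An AF episode in that interval is dated late if it is still present when recording resumes, and lost if it has ended. Section 1 notes that POAF can be self-limited and the threshold is only 30 seconds, so complete loss is realistic.

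The loss falls on a particular group. The composite used for the sample size counts any stay over 5 days as an event, so AF detection decides the result only for shorter stays. In those patients the gap comes soonest after surgery.

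Two smaller consequences follow. The visit window opens 14 days after discharge whenever wear began, so a late-started monitor may be handed in before it has run its course. AF burden, a secondary outcome taken from the monitor, would also cover different postoperative days in weekday and weekend patients.

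**Working it through.** **Inputs from the documents.** Event rates 50% and 20%, two-sided alpha 0.05, 80% power, unpooled Z test, 10% dropout, 80 patients (Section 6); visit from 2 weeks after discharge (Section 5); POAF usually on days 2 to 4 (Section 1).

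**Assumptions, because the documents give no figure.** Weekend share w = 2/7; delay g from discharge to wear of 1 to 7 days; share s of first events that occur after discharge of 10% to 40%, evenly over 14 days and alike in both arms; every event in the gap missed.

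**Step 1: the plan's own figure.** n = (0.5×0.5 + 0.2×0.8)(1.960 + 0.842)² / 0.30² = 35.76, so 36 per arm. 36/0.9 = 40 per arm, 80 in total. The stated size is reproduced, and power at 36 per arm is 80.3%. Section 6 attaches the 50% to the treatment arm, against the hypothesis, but the two-sided size is the same either way.

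**Step 2: patients affected.** 80 × 2/7 = 22.9, about 23. At half that weekend share, 80 × 1/7 = 11.4. Not all have a first event at stake. With a mean event rate of (50% + 20%)/2 = 35%, the number still event-free at discharge is 22.9 × (1 − 0.35(1 − s)): 15.7 for s = 10% and 18.1 for s = 40%, or about 16 to 18.

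**Step 3: wear and cover.** Wear at a day-14 visit is 14 − g. Full wear needs return no earlier than day 14 + g.

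| Delay g (days) | Wear at day-14 visit | First 14 days uncovered, g/14 | Averaged over cohort, w×g/14 | Earliest return for full wear |
|---|---|---|---|---|
| 1 | 13 | 7% | 2% | day 15 |
| 3 | 11 | 21% | 6% | day 17 |
| 5 | 9 | 36% | 10% | day 19 |
| 7 | 7 | 50% | 14% | day 21 |

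A monitor fitted at discharge (g = 0) has its full 14 days by the earliest visit, so early return is a problem only after a delayed start.

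**Step 4: events and power.** Missed share m = s × w × g/14. Both event rates are multiplied by (1 − m), and power is recomputed at 36 per arm.

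| s | g = 1: missed, power | g = 7: missed, power |
|---|---|---|
| 10% | 0.2%, 80.1% | 1.4%, 79.3% |
| 20% | 0.4%, 80.0% | 2.9%, 78.3% |
| 40% | 0.8%, 79.7% | 5.7%, 76.3% |

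**Step 5: a ceiling.** Events may cluster soon after discharge rather than spread evenly. If every post-discharge first event in weekend patients were missed, m = s × 2/7, which is 2.9% for s = 10% and 11.4% for s = 40%. At 11.4% the rates become 44.3% and 17.7%, and power is 72.1%. This is a bound, not an expectation.

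**The case against.** The strongest reply is that little is lost. Section 1 puts POAF mainly on days 2 to 4 with a peak on day 2, when most patients would still be on telemetry. Section 5 says that collection or mailing follows at once, and collection could be quick. Day of the week is not tied to arm. All this stands, and it keeps the estimated effect small. It does not close the gap, since a mailed device needs some time to arrive and no limit is set.

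Four stronger readings are tempting, and the documents do not support them.
- A reader might infer that gap days are counted as AF-free. Section 6 names Kaplan-Meier curves but gives no rule for unobserved time. The handling is unspecified, not stated to be wrong.
- A reader might take the primary endpoint to be affected on any reading. Under Section 2 only the secondary endpoint is.
- A reader might conclude that a two-week visit always truncates late-started wear. Mail-back is allowed and the visit may be as late as one month, so truncation can happen but need not.
- A reader might expect the gap to favour LLTS. That requires LLTS to change discharge timing. Section 5 says that the operating physician is told the allocation and leaves postoperative care to the primary team; it does not say that those who decide discharge know the arm. Section 6 has AF timing read by blinded physicians. Loss that is equal in both arms shrinks the difference rather than favouring either arm.

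**Conclusion.** The point holds as a stated procedure that gives poorer data than an easy alternative. Followed as written, it leaves rhythm unrecorded after weekend discharges, within the primary AF outcome of Section 6 or the secondary endpoint of Section 2, and it permits return of a late-started monitor before 14 days of wear.

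The likely size is small: 0.2% to 5.7% of events missed and at most about 4 points of power, on the assumed weekend share, delays, post-discharge event share and even spread. The count of 23 is an upper figure under an even spread of discharges. It includes patients who have already had an event, so it is not a count of lost outcomes. These figures assume equal loss in both arms. Differential loss remains possible if treatment alters length of stay, but nothing in the documents establishes its presence or direction. The change is worth making, and the sample size need not be revisited on this account.

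**What to change.** Amend Section 5 and footnote g together.

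1. Fit the monitor on the last weekday before a possible weekend discharge, while the patient is still on telemetry. Where existing staff can do it, allow fitting from ward stock before the patient leaves; this should be optional, since it may otherwise need extra weekend staffing.
2. Set return, by mail or at the visit, as on or after 14 days of wear counted from application.
3. Record the date and time that each monitor was started and stopped.
4. State in Section 6 that unmonitored days are unobserved, handled for example by interval censoring or a sensitivity analysis.
5. Define AF burden over the same post-discharge window in all patients.
6. Reconcile Sections 2 and 6 on whether AF in the 14-day period is primary or secondary.

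**Cost.** Protocol wording, two dates per patient and, if the option is used, a small stock of monitors; no added visit. Early fitting means predicting weekend discharges, and 1 to 3 monitor days would overlap telemetry. Those patients then have 14 − 3 = 11 to 14 − 1 = 13 days of post-discharge cover, so a common window for AF burden could be no longer than the first 11 days. Items 2 to 4 are still needed for anyone whose monitor starts late.

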6. STATISTICAL PLAN AND CONSIDERATIONS

Primary Outcome:

1. Time to the first episode of AF >30 seconds during inpatient admission or within 14-day monitoring period

- a. In hospital: full-disclosure telemetry
- b. Time to AF will be assessed by physicians blinded to randomization
- 2. Extended hospitalization of >5 days

Secondary Outcomes:

- 1. Overall AF burden, as assessed by 2 week monitor (CardioNet or Zio Patch) upon discharge
- 2. Inflammatory markers: C-reactive protein (ordered if clinically indicated)
- 3. Actionable AF: antiarrhythmic use (including rate-control meds), CDV, anticoagulation, use of inotropes for BP support during AF
- 4. Stroke or transient ischemic attack (TIA)
- 5. All cause of mortality

Sample size estimation:

Assuming a two-armed study with composite endpoint of occurrence of AF or >5 days hospitalization, whereby the treatment group will have 50% likelihood of the event occurring and a control group will have 20% likelihood of the event occurring, as well as a 10% dropout rate, we will be able to detect differences in 80 patients (40 in each arm). Under these assumptions and using two-sided Z-Test with unpooled variance to compare the changes between these two groups, we will have 80% power ($\alpha=0.05$) to detect a difference between the group proportions of 0.30. PASS software Version 15 (NCSS, LLC, Kaysville, UT) was used to calculate the statistical power.

Statistical methods:

Patients will be studied based on the randomization allocation. Patients who refuse to continue with study treatment (i.e. they refuse to wear ear clip) during time of therapy will be analyzed as intention-to-treat per allocation group. Fisher's exact or the Chi-Square test will be used for categorical variables, and continuous parameters will be compared by the two-tailed unpaired Student's t test and the F test for analysis of variance (ANOVA), as needed. Kaplan-Meier method will be used for computing the event free survival curves. Each strategy will be compared within this cohort of patients for its impact on percent incidence of POAF and length of stay. Multiple logistic regression and multiple regressions using the Cox proportional hazards model will be performed to determine the independent association of each of the demographic variables with clinical outcome.

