Transcutaneous low-level tragus stimulation (LLTS), however, has recently emerged as a novel, entirely noninvasive means to achieve vagal nerve stimulation, which achieves anticholinergic and antiadrenergic effects.¹¹ The auricular branch of the vagus nerve localizes to the skin near the anterior protuberance of the outer ear, called the tragus. LLTS has been shown to significantly suppress AF inducibility, reduce overall AF duration, and reduce the production of inflammatory cytokines (i.e., TNF-alpha and C-reactive protein) in acute studies.¹²⁻¹⁵ Furthermore, it may have additional benefits in inducing autonomic remodeling, as well as reducing ventricular arrhythmia.¹⁶ The Parasym device delivers LLTS through the skin via the outer ear (see Appendix A, Figures 1-2). It has been used in a variety of medical treatments, including tinnitus, depression, anxiety, and rheumatoid arthritis. We seek to evaluate the role of LLTS in preventing POAF, reducing AF duration, reducing average length of stay, and reducing overall arrhythmia incidence after cardiac surgery.

B. OBJECTIVES

We hypothesize that:

- a. In patients undergoing cardiac surgery (i.e., CABG and/or valve surgery), new-onset POAF is common
- b. LLTS is a simple, noninvasive and effective means to reduce the incidence of POAF, reduce overall AF duration, and reduce incidence of significant ventricular arrhythmias (i.e., nonsustained or sustained VT/VF)
- c. Use of LLTS in the inpatient setting leads to reduced overall AF and reduced AF duration in the 30-day period after cardiac surgery

Specific aims:

Aim 1: To determine the overall rate of successful LLTS in the inpatient setting. Patients randomized to LLTS will undergo continuous stimulation for two inpatient days. Tolerance of LLTS versus sham will be assessed.

Aim 2: To assess the impact of LLTS on acute and short-term outcomes. Acute outcomes include the incidence of inpatient POAF during the index hospitalization, length of hospital stay, overall AF duration, and incidence of nonsustained or sustained VT/VF. Short-term outcomes include incidence of AF as assessed by 14-day monitor (i.e. Zio patch or CardioNet event monitor) upon discharge.

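### Sections 2 and 6 define the primary endpoint differently (AF on the 14-day monitor is secondary in one and primary in the other), and no single test is named for it

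*Combined protocol and SAP*

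**What the plan says.** The primary endpoint is described in several places in the combined protocol and SAP.

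- **Section 2, primary endpoints.** "Primary clinical endpoint is time to inpatient AF (length of stay >5 days", where the parenthesis is not explained. The next sentence reads "Secondary endpoint is any occurrence of AF during 14 day post procedure monitoring". Under the same heading stands "Arrhythmia occurrence (i.e., AF, nonsustained VT, VT or VF requiring device therapy) will be documented throughout the study period", with no word on whether this is primary.
- **Section 1.B, Aim 2.** Inpatient and monitor AF are separate outcomes here too: "Acute outcomes include the incidence of inpatient POAF during the index hospitalization, length of hospital stay", and then "Short-term outcomes include incidence of AF as assessed by 14-day monitor".
- **Section 6, Primary Outcome.** Item 1 is "Time to the first episode of AF >30 seconds during inpatient admission or within 14-day monitoring period". Item 2 is "Extended hospitalization of >5 days". Nothing says whether the two are joined or tested apart.
- **Section 6, sample size.** The calculation is for a "composite endpoint of occurrence of AF or >5 days hospitalization", by a two-sided Z-test with unpooled variance.
- **Section 6, statistical methods.** Neither the composite nor the Z-test appears. The arms are compared on POAF incidence and length of stay. Fisher's exact or chi-square may be used for any categorical variable, with no rule for choosing. Kaplan-Meier curves come with no between-arm test. The logistic and Cox models are described only for demographic variables. The Study Summary leaves the same choices open.

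**The concern.** Two current rules classify the same patient differently. Someone who leaves hospital within 5 days in sinus rhythm and has a first AF episode at home is a primary event under Section 6 and only a secondary event under Section 2.

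The form of the endpoint is also unsettled. It could be time to AF, or the binary composite on which the trial was sized, and the test is open as well. Followed as written, the plan would allow the event definition and the test to be chosen after the data are seen. In an 80-patient trial, that leaves the primary p-value without a clear meaning.

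**Working it through.** **Inputs (Section 6, sample size):** event rates 50% and 20%, two-sided alpha 0.05, power 80%, unpooled variance, 10% dropout, 40 per arm. I take 50% as control and 20% as LLTS. The text prints them the other way round, and power is the same either way.

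**1. The plan's own figure.**
n per arm = (1.96 + 0.8416)² × (0.5×0.5 + 0.2×0.8) / 0.30² = 35.76, so 36. Then 36/0.9 = 40 per arm, 80 in total. Normal-approximation power at 36 is 80.3%. The stated N reproduces for the binary composite with the unpooled Z-test.

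**2. Power under each candidate test.** Full binomial enumeration, 50% against 20%, two-sided 0.05:

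| Evaluable per arm | Unpooled Z | Uncorrected chi-square | Fisher's exact |
|---|---|---|---|
| 36 | 80.5% | 78.7% | 69.6% |
| 40 (no dropout) | 82.6% | 81.7% | 74.9% |

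The two tests the methods paragraph names differ by 9.0 points at 36 per arm and 6.7 points at 40 (from unrounded values).

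**3. One result, two conclusions.** Take 18/36 against 9/36. The pooled rate is 27/72 = 0.375 and the difference 0.25.
- Chi-square: z = 0.25/√(2×0.375×0.625/36) = 2.19, p = 0.028.
- Unpooled Z: z = 0.25/√((0.25 + 0.1875)/36) = 2.27, p = 0.023.
- Fisher's exact: p = 0.0505.

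At the design rates with 36 per arm, chi-square is significant and Fisher is not in 9.0% of trials.

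**4. Exact type I error, common event rate 20% to 50%.**

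| Evaluable per arm | Unpooled Z | Chi-square | Fisher's exact |
|---|---|---|---|
| 36 | 5.2–6.2% | 4.5–5.4% | 2.5–2.8% |
| 40 | 5.2–5.7% | 4.8–5.7% | 2.8–3.3% |

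**5. The AF window.** The documents give no AF rate for inpatient telemetry alone or for telemetry plus monitor, so the effect of the window on the event rate cannot be computed. As an illustration only, keep the 60% relative reduction implied by 50% against 20% (assumption) and use the formula in step 1:

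| Rates | n per arm | After 10% dropout | Total |
|---|---|---|---|
| 60% / 24% | 25.6, so 26 | 29 | 58 |
| 50% / 20% | 35.76, so 36 | 40 | 80 |
| 45% / 18% | 42.5, so 43 | 48 | 96 |
| 40% / 16% | 51.02, so 52 | 58 | 116 |

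At 36 per arm, exact power is 73.5% (unpooled Z) or 71.9% (chi-square) for 45%/18%, and 65.8% or 63.8% for 40%/16%.

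**The case against.** The best defence is that the intended endpoint can be inferred. The composite's components are the two items listed as primary in the same section, item 1 supplies the 30-second threshold and the window, and Section 2 also sets AF beside a stay over 5 days. This has force: the missing link is a drafting gap rather than a contradiction. It does not remove the conflict over the window, and it does not supply a test.

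Second, the Fisher figure is a worst case. The wording is generic for all categorical variables. At the design rates the expected cells are 36 × 0.35 = 12.6 and 36 × 0.65 = 23.4, so the usual small-count reason for Fisher is absent. Chi-square and unpooled Z differ by only 1.8 points at 36 per arm. This is fair, and the 69.6% applies only if Fisher is used. The plan still gives no rule that excludes it.

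Third, the power figures measure the choice of test, not the choice of window. That is correct. The window's effect is unquantified, and event rates could move either way.

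Fourth, the ventricular arrhythmia item is weak evidence. The text says only that these events will be documented, and the same heading contains an item labelled secondary. I treat its status as a point to clarify.

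Finally, inflated familywise error would arise only if items 1 and 2 were tested separately with either able to win. The plan does not say that, and I do not claim it.

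**Conclusion.** The concern holds, and the plan is wrong as written on this point. It should be corrected before any outcome is compared by arm. The decisive facts are the contradiction between Sections 2 and 6 over monitor AF, which no other section resolves, and the lack of one named test for one named primary endpoint.

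N = 80 is not wrong for the endpoint and test on which it was computed. The 80% power is not delivered under Fisher's exact, even with no dropout. These figures assume that 50% and 20% apply to the composite under whichever AF window is chosen, which the documents do not establish.

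**What to change.** State one primary endpoint in the same words in Section 2, in Section 6 and in the sample-size paragraph, with one two-sided test at 0.05. Make everything else secondary. The option closest to the sizing is the binary composite of AF longer than 30 seconds or a stay over 5 days. For that option:

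- Choose the AF window: inpatient telemetry only, as in Section 2, or including the monitor, as in Section 6.
- Say when the 5-day count starts.
- Name either the uncorrected chi-square test or the unpooled Z-test.
- Say how a death or withdrawal before day 5 without AF is scored. The plan is silent, and read literally an early death meets neither component and would count as event-free.
- If monitor AF is included, say how a patient with no monitor data is scored.
- Confirm that 50% and 20% apply to the chosen window, or restate N.

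If time to first AF is chosen instead, name the log-rank test and recompute power from an AF-only rate, since the sample-size paragraph gives none. In either case, say whether the arrhythmia endpoint in Section 2 is secondary.

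**Cost.** This is wording only, with no new data and N unchanged, if the sponsor confirms the rates. Otherwise N changes; the illustrations above run from 58 to 116. Some outcomes lose primary status. With chi-square, the restated power is 78.7% at 36 per arm. The unpooled Z-test keeps 80% but its exact type I error is above 5% over the range examined, and chi-square also exceeds 5% at some rates.

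The composite has a further weakness. Blinded assessment is stated for time to AF but not for length of stay, and the operating physician knows the allocation (Section 5). The documents do not say who decides discharge, so this is a possible influence and not a demonstrated one.

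### CRP is compared between arms, but Section 6 and the schedule limit it to patients whose clinicians order it, while Section 5 reads as collection in everyone: the comparison is at risk of bias and its precision is unknown

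*Combined protocol and SAP*

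**What the plan says.** The protocol states the CRP collection rule in three places.

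- **Section 6, Secondary Outcomes, item 2**, under inflammatory markers: "C-reactive protein (ordered if clinically indicated").
- **Section 15.C, schedule of events**: the row "C-Reactive Protein Blood Test" is marked for Day 0 and for post-operative days 1–2. Both marks carry footnote f, "If clinically indicated". The screening column is empty.
- **Section 5, periprocedure care**: "Blood will be collected for C-reactive protein measurement to assess inflammation per routine lab assessments". The condition does not appear here.

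For analysis, Section 6 says that "continuous parameters will be compared by the two-tailed unpaired Student's t test", with ANOVA as needed. Patients who stop wearing the clip stay in their allocated group. No missing-data method is given.

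On who knows the allocation, Section 2 says "Patients will be randomized, to LLTS versus sham procedure, and remain blinded to their treatment allocation", and the summary calls the trial single-blind. Section 5 adds "Operating physician will be informed of patient randomization allocation to facilitate planning of procedure". Blinded assessment is specified only for time to AF.

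**The concern.** A value obtained only when a clinician asks for it is a post-randomisation selection. The reasons for asking, which the protocol does not define, may be related to the CRP level itself. If stimulation lowers CRP, fewer LLTS patients would then be tested, and those tested would be the ones with higher values. If ordering habits differ between arms for any other reason, the tested groups differ even when stimulation does nothing. In both cases the t test no longer compares the groups that randomisation created.

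Keeping patients in their allocated group does not solve this, because a patient without an order contributes no value.

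At stake is the only inflammatory marker the trial plans to measure. Section 1.A cites reduced inflammation as one of the effects of LLTS. Under the conditional rule, neither a null nor a positive CRP result could be interpreted with confidence.

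**Working it through.** **The plan's own figure.** Section 6 gives no calculation for CRP. Its sample size for the composite endpoint (50% against 20%, two-sided α 0.05, 80% power, unpooled Z test, 10% dropout) supplies the numbers per arm:

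n = (0.5×0.5 + 0.2×0.8) × (1.960 + 0.842)² / 0.30² = 0.41 × 7.85 / 0.09 = 35.8, rounded up to 36; 36 / 0.90 = 40 per arm, 80 in total.

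The stated 80 is reproduced. Below, 36 is the number per arm after dropout and 40 the number randomised.

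**Assumptions.** The documents give no SD, expected effect or ordering rate for CRP. CRP is therefore expressed in SD units and taken as normal. The true effect of 0.6 SD, the ordering rates and the dependence of ordering on CRP are all assumed.

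**1. Fewer values, no selection.** Detectable difference at 80% power = 2.802 × √(2/m), where m is the number measured per arm:

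- all 36 measured: 2.802 × √(2/36) = 0.66 SD
- half, m = 18: 0.93 SD
- a quarter, m = 9: 1.32 SD

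**2. Same ordering rule in both arms, ordering related to CRP.** Model: log-odds of an order = a + b × CRP (in SD units), with a and b common to both arms. The true LLTS-minus-sham difference is −0.6 SD. Power is for the unpaired t test: exact for complete sampling, otherwise from 8,000 simulated trials per cell.

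| Dependence, b | Measured, sham / LLTS | Expected difference | Power, 36 / 40 per arm |
|---|---|---|---|
| everyone measured | 100% / 100% | 0.60 SD | 71% / 75% |
| 0.5 (weak) | 87% / 83% | 0.58 SD | 63% / 67% |
| 1 | 50% / 38% | 0.50 SD | 30% / 33% |
| 2 (strong) | 35% / 20% | 0.36 SD | 16% / 16% |

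Attenuation runs from (0.60 − 0.58)/0.60 = 3% to (0.60 − 0.36)/0.60 = 40%. In the last row, 36 per arm leaves about 36 × 0.35 = 13 sham and 36 × 0.20 = 7 LLTS values.

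**3. No true effect, same rule.** The expected difference is 0, and the t test rejects in about 5% of simulated trials.

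**4. No true effect, ordering rates differ by arm.** If the tendency to order has correlation ρ with CRP and a fraction f of an arm is tested, the mean among those tested is ρ × φ(z)/f, where φ is the standard normal density and z the cut-off that leaves fraction f above it. For f = 0.60 and 0.40, φ(z) = 0.386 in both:

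difference = ρ × (0.386/0.40 − 0.386/0.60) = ρ × (0.966 − 0.644) = 0.322ρ

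This is 0.10, 0.16 and 0.23 SD for ρ = 0.3, 0.5 and 0.7. The arm tested less often appears to have the higher CRP, so the sign depends on which arm that is.

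**The case against.** Several points on the other side stand.

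- **A reader might infer that CRP will be mostly unmeasured.** The documents do not support that. No ordering rate is given, and Section 5 can be read as collection in all patients with routine bloods. The range must therefore extend to near-complete sampling, where the loss is small.
- **A reader might infer that the comparison is biased as it stands.** It is at risk of bias. With no true effect and the same rule in both arms there is none, and the false-positive rate holds. Under a common rule in the model above, a true effect is attenuated. A spurious effect needs ordering to differ by arm.
- **The route from unblinding to ordering is indirect.** The person told the allocation is the operating physician, whereas Section 5 says "Postoperative care for the cardiac surgical patient will be performed as per routine standard of care by the treating primary team". Nothing states that whoever orders CRP knows the arm. Equally, nothing keeps that person blinded.
- **CRP is peripheral.** It appears in no hypothesis and in neither aim of Section 1.B.
- **The lack of a pre-operative CRP is not an error.** With complete sampling, an unadjusted comparison would be valid.

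These points limit the size and importance of the concern. They do not remove it: Section 6 and footnote f state a conditional rule, Section 5 states a different one, and the analysis does nothing to offset selection.

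**Conclusion.** The concern holds as a contradiction about who has CRP measured and, under the conditional rule, as a between-arm comparison that randomisation no longer protects. How much is lost cannot be determined from the documents. With an assumed effect of 0.6 SD, the result ranges from close to harmless to a comparison with little chance of detecting anything, as the table shows. A spurious difference of 0.10–0.23 SD in either direction is possible if ordering runs at 60% against 40% by arm, but the documents neither establish nor exclude such an imbalance. The contradiction and the selection risk are certain from the text; the figures are illustrations that depend on the assumed models. Only one mechanistic secondary outcome is affected. The primary outcome and the sample size are not. The point should be corrected, but it does not threaten the trial's main conclusion.

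**What to change.** Reconcile Section 5, Section 6 and schedule footnote f so that all three state one rule. Amending Section 6 alone would leave the contradiction in the schedule. Then choose one of two options.

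- **(a) Measure everyone.** Remove the condition from Section 6 and footnote f, and measure CRP in every randomised patient at the times already scheduled (Day 0 and post-operative days 1–2), added to routine draws. State which value is compared and how missing values are handled. Cost: an amendment and two or three assays per patient, that is 160 to 240 assays for 80 patients. A pre-operative value with baseline adjustment would add precision but is optional, and it may need a further sample because Section 5 describes no pre-operative CRP draw.
- **(b) Keep clinically driven ordering.** Align the Section 5 wording with it, report CRP descriptively with the number measured in each arm, and draw no between-arm inference. Cost: a text change only.
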